6.3. Subgroup Analyses

Subgroup analyses of endpoints related to CDAI and PRO2 will be performed for the induction non-responders (see Section 3.4), overall, and by prior exposure to biologic agents.

For these analyses, an imputation approach will be used for missing data due to premature discontinuation from the study (for any reason, except due to study closure). [REDACTED]

[REDACTED] In analyses of continuous CDAI/PRO2 scores, missing scores after discontinuation will be imputed by the LOCF approach using the most recent available value from all previous analysis visits.

6.4. [REDACTED]

[REDACTED]

[REDACTED]

[REDACTED]

[REDACTED]

[REDACTED]

[REDACTED]

[REDACTED]

[REDACTED]

[REDACTED]

[REDACTED]

[REDACTED]

[REDACTED]

[REDACTED]

[REDACTED]

[REDACTED]

[REDACTED]

[REDACTED]

[REDACTED]

[REDACTED]

[REDACTED]

[REDACTED]

[REDACTED]

[REDACTED]

[REDACTED]

[REDACTED]

[REDACTED]

[REDACTED]

[REDACTED]

[REDACTED]

[REDACTED]

[REDACTED]

[REDACTED]

[REDACTED]

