### **3.6. Disease Worsening Criteria**

Subjects meeting the following criteria should be considered to be discontinued from the study.

- Any subject with significant disease worsening or lack of response to therapy based on investigator judgment may discontinue study drug at any time during the LTE
- Disease worsening based on change in CDAI score may also be used to guide discontinuation of the subject: eg, increase in CDAI  $\geq 100$  from Day 1 in present study and CDAI  $> 220$  at 2 consecutive visits.
  - The disease worsening visits may include unscheduled visits (eg, a study visit followed by an unscheduled visit, or 2 sequential unscheduled visits).
- If a subject experiences significant worsening of underlying CD, which requires any of the prohibited medications (refer to Section 5.4.2), or surgical intervention at any point during the study, treatment discontinuation should be considered at investigator's discretion, in consultation with medical monitor if feasible (refer to Section 3.5.2).
- A stool sample will be obtained for culture for pathogenic bacteria, ova and parasite evaluation, and *C. difficile* toxin assay, when a subject becomes symptomatic, including worsening or return of disease activity.

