3.8.2. Analysis Visit Windows

Subject visits might not occur on protocol-specified days. Therefore, for the purpose of analysis, observations will be assigned to analysis windows.

The analysis windows for CDAI, PRO2, vital signs, weight, hematology, and chemistry are provided in Table 3-1. The analysis windows for lipid profile, serum immunoglobulin, [REDACTED] [REDACTED] are provided in Table 3-2. The analysis windows for [REDACTED]

Table 3-1. Analysis Visit Windows for CDAI, PRO2, Vital Signs, Weight, Hematology and Chemistry

Nominal Visit	Nominal Study Day	Visit Window Study Day	
		Lower Limit	Upper Limit
Baseline	1	(none)	1
Week 2	15	2	22
Week 4	29	23	57
Week 12	85	58	127
Week 24	169	128	211
Week 36	253	212	295
Week 48	337	296	379
Week 60	421	380	463
Week 72	505	464	547
Week 84	589	548	631
Week 96	673	632	715
Week 108	757	716	799
Week 120	841	800	883

Nominal Visit	Nominal Study Day	Visit Window Study Day	
		Lower Limit	Upper Limit
Week 132	925	884	967
Week 144	1009	968	1051
Week 156	1093	1052	1135
Week 168	1177	1136	1219
Week 180	1261	1220	1303
Week 192	1345	1304	1387
Week 204	1429	1388	1471
Week 216	1513	1472	1555
Week 228	1597	1556	1639
Week 240	1681	1640	1723
Week 252	1765	1724	1807
Week 264	1849	1808	1891
Week 276	1933	1892	1975
Week 288	2017	1976	2059
Week 300	2101	2060	2143
Week 312	2185	2144	2227
Week 324	2269	2228	2311
Week 336	2353	2312	2395
Week 348	2437	2396	2479
Week 360	2521	2480	2563
Week 372	2605	2564	2647
Week 384	2689	2648	2731
Week 396	2773	2732	2815
Week 408	2857	2816	2899
Week 420	2941	2900	2983
Week 432	3025	2984	≥ 3025

CDAI = Crohn's Disease Activity Index; PRO2 = patient reported outcome consisting of 2 items: abdominal pain severity and liquid stool frequency

Table 3-2. Analysis Visit Windows for Lipid Profile, Serum Immunoglobulin,

Nominal Visit	Nominal Study Day	Visit Window Study Day	
		Lower Limit	Upper Limit
Baseline	1	(none)	1
Week 24	169	2	253
Week 48	337	254	421
Week 72	505	422	589
Week 96	673	590	757
Week 120	841	758	925
Week 144	1009	926	1093
Week 168	1177	1094	1261
Week 192	1345	1262	1429
Week 216	1513	1430	1597
Week 240	1681	1598	1765
Week 264	1849	1766	1933
Week 288	2017	1934	2101
Week 312	2185	2102	2269
Week 336	2353	2270	2437
Week 360	2521	2438	2605
Week 384	2689	2606	2773
Week 408	2857	2774	2941
Week 432	3025	2942	≥ 3025

3.8.3. Selection of Data in the Event of Multiple Records in an Analysis Visit Window

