Depending on the statistical analysis method, single values may be required for each analysis window. For example, change from baseline by visit usually requires a single value, whereas a time-to-event analysis would not require 1 value per analysis window.

If multiple valid, nonmissing measurements exist in a postbaseline analysis window, records will be chosen based on the following rules if a single value is needed:

- The record closest to the nominal day for that visit will be selected.
- If there are 2 records that are equidistant from the nominal day, the later record will be selected.
- If there is more than 1 record on the selected day, the average will be taken for continuous data and the worse severity will be taken for categorical data, unless otherwise specified.

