Calculation of CDAI and PRO2 Scores for Baseline and Post-baseline Visits

The calculations of CDAI and PRO2 scores for baseline and post-baseline visits are specified below:

- 1) The Day 1 visit date will be used as the anchor day for baseline and following visit dates will be used as the anchor day for post-baseline visits. The visit date for each analysis visit will be selected as the anchor day among all scheduled visits and unscheduled visits where CDAI were assessed within the analysis window as defined in Section 3.8.2. Only diary data collected on evaluable days within a 10-day window which starts 10 days prior to the selected visit date (V-Day 1) and ends on the day prior to V-Day 1 will be used for calculation.
- 2) If there are 7 or more evaluable records within the 10-day window, take the **sum** of the 7 evaluable records closest to V-Day 1 for the corresponding CDAI subject-reported component. For the corresponding PRO2 component, take the **average** of the 7 evaluable records within the 10-day window closest to V-Day 1.
 - a) If there are 4 or more (but less than 7) evaluable records within this 10-day window, the average of the available records will be taken, and then multiplied by 7 for the corresponding CDAI patient-reported component. For the corresponding PRO2 component, the average of the available records will be taken.
 - b) If subjects do not have at least 4 evaluable records within this 10-day window, the corresponding CDAI patient-reported component, and the corresponding PRO2 component will not be calculated and will be considered as missing for that visit.

A schema of this approach and some examples are included below for further explanation:

Figure 1. Selection of Diary Data for the Calculation for Baseline and Postbaseline Visits

[figure not shown]

Table 11-3. Calculation of CDAI Patient-Reported Outcome Components and PRO2 Scores for Baseline and Post-baseline Visits

Example	Diary Day Looking Backwards from Visit Date (V-Day)										Days for Calculation	Sum of 7 Days (CDAI Patient-Reported Component)	Average of 7 Days (PRO2)
	-10	-9	-8	-7	-6	-5	-4	-3	-2	-1			
Diary Subscore 1	1	2	2	M	0	1	2	2	1	X	-2,-3,-4,-5,-6,-8,-9	10.0	1.4
Diary Subscore 2	M	M	1	M	X	IL	2	2	1	M	-2,-3,-4,-8	10.5	1.5
Diary Subscore 3	M	M	1	X	IL	M	M	2	1	M	-2,-3,-8	Missing	Missing
Diary Subscore 4	0	M	2	2	1	0	M	2	X	IL	-3,-5,-6,-7,-8,-10	8.2	1.2

M = Missing; IL = Ileocolonoscopy day; X = non-evaluable (due to preparation for ileocolonoscopy).

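### LOCF in SAP 6.3 carries the one score kept per visit window, so an Early Termination or unscheduled score taken after a scheduled visit in the same window is usually dropped in favour of the earlier one

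*SAP*

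**What the plan says.** SAP 6.3 applies LOCF to continuous CDAI and PRO2 scores in the induction non-responder subgroup when a subject leaves the study early for any reason other than study closure: "missing scores after discontinuation will be imputed by the LOCF approach using the most recent available value from all previous analysis visits". The source is the analysis visit, not the assessment.

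Four other rules decide what an analysis visit contains:

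- **Windows (SAP 3.8.2, Table 3-1).** Because visits may not fall on planned days, "observations will be assigned to analysis windows". The Week 24 row reads "Week 24 169 128 211": nominal day, lower limit, upper limit. ET has no row of its own, so an ET record enters a window by study day.
- **Selection (SAP 3.8.3).** "The record closest to the nominal day for that visit will be selected" The tie rule is: "If there are 2 records that are equidistant from the nominal day, the later record will be selected".
- **Scoring (SAP Appendix 2).** "The visit date for each analysis visit will be selected as the anchor day among all scheduled visits and unscheduled visits" with a CDAI assessment in the window. Only diary entries from the ten days before that anchor are used.
- **Source of scores (SAP Appendix 2).** The diary vendor's own calculated scores are excluded from the analysis.

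Protocol 6.6 and the Study Procedures Table collect CDAI and PRO2 at the ET visit. Protocol 3.5.2 asks withdrawing subjects to complete that visit.

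**The concern.** LOCF is meant to carry the last observation. Under these rules the value carried can be an earlier one, although a later score was collected at exit. Whether the exit score counts depends on which side of a window boundary the ET visit falls, which has no clinical meaning.

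The exit score matters for this imputation because worsening or lack of response is a named reason for leaving at any time (Protocol 3.6). If a subject deteriorates between the scheduled visit and the exit, the better, earlier score stands in for that subject at every later visit. SAP Section 10 shows that Version 2.0 added these imputation rules to understand this subgroup better.

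**Working it through.** **Step 1. Reproduce the windows.** Each upper limit should be the midpoint between adjacent nominal days: (15+29)/2 = 22, (29+85)/2 = 57, (85+169)/2 = 127, (169+253)/2 = 211. These, and every later limit up to day 2983, agree with Table 3-1. The Week 12 window is days 58-127: 70 days, with 27 before and 42 after nominal. From Week 24 to Week 420 the windows are 84 days wide.

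**Step 2. One worked case.** A subject attends Week 24 on day 169.

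- ET on day 211 lies in the Week 24 window. The distances from nominal are 42 days (ET) and 0 days (scheduled). The scheduled visit is the anchor, the ET diary is not scored, and the day-169 score is carried to Week 36 and beyond.
- ET on day 212 lies in the Week 36 window (212-295) and is the only record there. It is scored, and carried from Week 48 on.

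**Step 3. Count the exit days on which the ET score loses,** with scheduled visits on time. The share is the number of days from the day after the visit to its window's upper limit, divided by the number of days between the two visits.

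| Interval | Exit days | Earlier window closes | Days lost | Share |
|---|---|---|---|---|
| Day 1 to Week 2 | 2-14 (13) | day 1 | 0 | 0% |
| Week 2 to Week 4 | 16-28 (13) | day 22 | 7 | 53.8% |
| Week 4 to Week 12 | 30-84 (55) | day 57 | 28 | 50.9% |
| Week 12 to Week 24 | 86-168 (83) | day 127 | 42 | 50.6% |
| Week 24 to Week 36 | 170-252 (83) | day 211 | 42 | 50.6% |

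In the 12-week intervals, a lost ET score is on average (1+42)/2 = 21.5 days newer than the score kept, and at most 42 days newer.

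**Step 4. Allow for visit windows and exit timing.** The documents give no exit times, so each pattern below is an assumption. The check simulated 10,000 exits per pattern, with scheduled visits uniformly early or late by up to 3 days (Weeks 2 and 4) or 7 days (later), as the protocol allows.

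| Assumed exit pattern | ET scores lost |
|---|---|
| Uniform, Weeks 12-24 | 45% |
| Uniform, days 2-337 or 2-673 | 44% |
| Uniform, first 12 weeks | 38% |
| Exponential, median 84-672 days | 44-46% |
| 25% / 50% / 75% / 100% of exits at a scheduled visit, rest uniform | 33% / 23% / 12% / 0% |

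By time since the scheduled visit (Week 12 or later), the share lost is 66% at 3-7 days, 85% at 8-14 days, 100% at 15-34 days, 54% at 35-49 days, and 0% at 50-76 days. With late or early visits, the lost score can be up to 42 + 7 = 49 days newer.

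**Step 5. Effect on the subgroup mean.** Shift = share imputed × share of ET scores lost × mean rise from the kept to the lost score. The documents fix none of these three terms, so no size follows from them.

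**The case against.** **The text can be read more kindly.** SAP 3.8.3 opens with a condition: "Depending on the statistical analysis method, single values may be required for each analysis window". Appendix 2 does not itself say how the anchor is chosen, and a programmer might take the most recent available value to include ET. Part of SAP 6.3 just before the LOCF sentence is also redacted. What stands is that the intention may be sound. But Appendix 2 yields one score per analysis visit, SAP 3.8.3 is the only visible rule for choosing among visits, and vendor scores are barred. On the visible text, an ET visit that is not the anchor has no score to carry.

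**Exits may cluster at scheduled visits.** CDAI is assessed and drug is dispensed there. If the ET visit is the scheduled visit, nothing is lost. This stands: a reader might infer that close to half of all ET scores are discarded, but that needs exits spread evenly between visits, and the possible range is 0% to 100%.

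**The kept score may already show worsening.** The example in Protocol 3.6 requires two consecutive visits, and "The disease worsening visits may include unscheduled visits". If a study visit and the unscheduled visit after it share a window, the retained study visit already meets the criterion. Subjects also leave because of infection, laboratory criteria, pregnancy or their own request (Protocol 3.5.2), with no reason to expect a rise. Both points stand and weaken the bias.

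**A tempting figure.** A reader might assume that 20-60% of the subgroup is imputed, half of ET scores are lost, and CDAI rises 50-100 points. That gives 0.20 × 0.5 × 50 = 5 to 0.60 × 0.5 × 100 = 30 points. With 23% lost, it gives 0.20 × 0.23 × 50 = 2.3 to 0.60 × 0.23 × 100 = 13.8. The documents supply neither the imputed share nor the rise, and the formula gives every leaver the same rise whatever the reason for leaving. Neither range should be quoted as a finding.

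**Unscheduled visits are not always lost.** Appendix 2 admits them as anchors. They are kept when they are alone in a window or nearer to nominal.

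**Conclusion.** The point holds on the wording of the plan. SAP 6.3, Table 3-1, SAP 3.8.3 and Appendix 2 together let LOCF carry a score that is not the last one observed, and a one-day difference in the ET date can decide it. If exits are spread evenly between 12-weekly visits, about 44-51% of ET scores are lost. The share is about 23% if half of exits occur at a scheduled visit, and 0% if all do.

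The direction is favourable to the imputed course only where scores rise before exit. The effect is smaller where the kept visit already showed worsening, or where the subject left for another reason. Its size cannot be derived from the documents.

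The reach is limited to continuous secondary scores in one descriptive subgroup. No hypothesis test is planned (SAP 1.3 and 3.5), and the primary endpoint is safety. A reader might extend the criticism to the by-visit summaries in SAP 6.2.2. Those use observed values, and letting the on-time record represent a nominal visit is the purpose of a window, so they are not in error.

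**What to change.** Two changes to the SAP:

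1. In 6.3, state that LOCF uses the last observed post-baseline CDAI or PRO2 score on or before discontinuation, including ET and unscheduled visits, whether or not that record was selected for a window.
2. In Appendix 2, derive a score for every visit with a CDAI assessment, so that this value exists. Selection of one record per window can stay as it is for the by-visit summaries, and SAP 6.2.2 needs no change.

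The cost is minor reprogramming. The scores' components are already collected at ET. SAP Section 1 provides for changes after finalisation to be documented in the study report.

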### 3.4. Duration of Treatment

Subjects will receive filgotinib or placebo until filgotinib becomes commercially available in the country or until the end of study (31 January 2025), whichever comes first. All subject visits, including the PTx visit, must be completed by 31 January 2025 at the latest. The maximum treatment duration will be approximately 7.5 years.

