1. INTRODUCTION

This statistical analysis plan (SAP) describes the statistical analysis methods and data presentations to be used in tables, figures, and listings (TFLs) in the interim analyses and clinical study report (CSR) for Study GS-US-419-3896 (GLPG0634-CL-310). This SAP is based on the study protocol Amendment 8 dated 2 December 2021 and the electronic case report form (eCRF). The SAP will be finalized before unblinding of Study GS-US-419-3895 (GLPG0634-CL-309), at which time this study will be unblinded. Any changes made after the finalization of the SAP will be documented in the CSR.

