1.2. Study Design

This is a long-term extension (LTE) study to evaluate the safety of filgotinib administered to subjects with CD. Some subjects will receive open-label drug and some will continue to receive the blinded study drug assigned in the parent study until subject's treatment in the corresponding parent study (GS-US-419-4015, GS-US-419-4016, or GS-US-419-3895) is unblinded. The duration of treatment is up to 432 weeks.

In general, subjects who fully complete a parent study blinded will continue blinded treatment at the same regimen in the present study on 200 mg filgotinib, 100 mg filgotinib, or placebo. Subjects who enroll from a parent study and receive blinded treatment in the GS-US-419-3896 study will have their GS-US-419-3896 treatment assignment unblinded when the parent study is unblinded. After the study unblinding, subjects will continue on the same dose of open-label filgotinib as they had been receiving in blinded treatment; whereas subjects on placebo treatment

will discontinue study drug and study participation. Subjects who exit a parent study due to disease worsening or failure to meet response or remission criteria will receive open-label 200 mg filgotinib, with the exception of US and Korea males in this category who were not considered biologic refractory who will receive open-label 100 mg filgotinib.

This study includes:

- Day 1
- Treatment Visits: Week 2, Week 4, Week 12, and then every 12 weeks thereafter
- Post-Treatment (PTx) safety assessments (30 days after the last dose of study drug) for subjects who complete all study treatment visits or discontinue early

For additional details, please see the Schedule of Assessments in [Appendix 1](#).

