4.2. Extent of Study Drug Exposure and Adherence

Extent of exposure to study drug will be examined by assessing the total duration of exposure to study drug and the level of adherence relative to the study drug regimen specified in the protocol.

If subjects are continuing study drug at the data cutoff date for an interim analysis, the data cutoff date will be used to impute the last dosing date for the calculation of duration of exposure to study drug and adherence to the study drug.

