6.2.2. Analysis of the Efficacy Endpoints

CDAI and PRO2

Descriptive statistics and 95% CI based on normal approximation will be used to summarize the absolute values and change from baseline values in CDAI and PRO2 scores by analysis visit and treatment group using observed values. Mean absolute values of each score with 95% CI will be plotted over all analysis visits by treatment group. Mean change from baseline values of each score with 95% CI will also be plotted.

[REDACTED]

[REDACTED]

[REDACTED]

[REDACTED]

[REDACTED]

[REDACTED]

[REDACTED]

[REDACTED]

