10. SAP REVISION

Revision Date (DD MMM YYYY)	Section	Summary of Revision	Reason for Revision
Original Gilead draft (11 February 2022)			
Draft 0.3 (11 July 2022)	Global	Editorial changes have been made throughout the SAP, where appropriate	To align with GLPG wording / template
	4.4	Added assessment of Ukrainian conflict impact	To better understand the Ukrainian conflict impact on subject disposition and missing data
	6.2	Added remission by CDAI and PRO2 as efficacy endpoints	To support the secondary endpoints.
	6.3, 7.1.8	Added subgroup analyses for efficacy endpoints and adverse events	To assess benefit/risk in subjects who completed the parent study and subjects who met protocol-specified efficacy discontinuation criteria
Draft 0.4 (1 Augustus 2022)	Global	Editorial changes have been made throughout the SAP, where appropriate	For clarification, based on team feedback
	5.2	Added baseline disease characteristics by subgroup	To complement the efficacy/safety subgroup analyses
	7.1.6	AEs will be presented ordered by total frequency, not alphabetically	Requested by medical writing
	7.5	Addition of ECG shift table	Requested by medical leads
	Global	Clarifications and corrections have been made throughout the SAP, where appropriate	Based on dry-run findings
Draft 0.5 (12 November 2022)	3.4	Update definition subgroups.	Based on internal discussion
	4.4.5	Replacing COVID impact indicator by listing of AEs related to COVID	The impact indicator is a Gilead-defined analysis. Not deemed valuable
	7.4	Addition of ATC level 2 in summaries of concomitant medications	Requested by medical leads
	7.5	ECG shift table replaced by frequency table	Baseline ECG not available in this study
	Title page	Update medical leader	

Final Version 1.0 (13 January 2023)	4.4	Reduction of planned analyses related to the impact of the Ukrainian conflict	Data availability
	5.2	Update prednisone dose categories	Requested by medical leads
	7.1.4	Added section on the handling of “action taken” information in the summaries of AEs	Clarification
	Appendix 5	Addition of MST lists based on the latest MedDRA version	For transparency on which lists were used at the time of analysis
Final Version 2.0 (1 August 2023)	3.2, 3.4, 5.1, 5.2, 6.3	Extension of analyses of baseline characteristics and efficacy endpoints in the subset of induction non-responders: by prior exposure, addition of imputation rules	For better understanding of this specific subgroup

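### Unless redacted text caps it, the SAP 6.3 LOCF rule would weight late-visit CDAI/PRO2 means in induction non-responders toward dropouts, beyond what LOCF does by itself

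*SAP*

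**What the plan says.** SAP 6.3 covers CDAI and PRO2 endpoints in the induction non-responders, overall and by prior biologic exposure. On missing scores it states that "an imputation approach will be used for missing data due to premature discontinuation from the study (for any reason, except due to study closure"). After two redacted blocks, the paragraph ends with the rule for continuous scores: "missing scores after discontinuation will be imputed by the LOCF approach using the most recent available value from all previous analysis visits". SAP section 10 shows that this arrived with Version 2.0 of 1 August 2023: "Extension of analyses of baseline characteristics and efficacy endpoints in the subset of induction non-responders: by prior exposure, addition of imputation rules".

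SAP Table 3-1 runs to Week 432. SAP 6.2.2 plots the score means over all analysis visits, but its full-population summary covers "change from baseline values in CDAI and PRO2 scores by analysis visit and treatment group using observed values".

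On duration, the SAP states "This SAP is based on the study protocol Amendment 8 dated 2 December 2021" and "The duration of treatment is up to 432 weeks". Protocol Amendment 9 (23 November 2022) had by then changed the stop. Under Protocol 3.4, treatment ends at commercial availability in the country or at the end of study on 31 January 2025, with the post-treatment (PTx) visit completed by that date. The same section adds: "The maximum treatment duration will be approximately 7.5 years".

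SAP 2.1 allows interim analyses. For subjects still on drug at an interim, SAP 4.2 says "the data cutoff date will be used to impute the last dosing date for the calculation of duration of exposure". The visible part of 6.3 has no matching limit.

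**The concern.** Two subjects start on the same day, so their possible follow-up is the same. One drops out early; the other stays on drug until the calendar stop. Read literally, the rule keeps the first in every later mean up to Week 432. The second has no score after closure and, by the closure exception, is not imputed. The same happens at an interim analysis: a subject still on treatment at the cutoff has not discontinued, while a dropout's score is filled past the cutoff.

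Ordinary LOCF keeps dropouts in the mean at their true cumulative share. Here the share would rise above that at every visit that some subjects cannot reach. Carried scores need not be neutral, because Protocol 3.6 lets disease worsening guide discontinuation (for example a CDAI rise of at least 100 from Day 1 with CDAI above 220 at two consecutive visits). A late trend in this subgroup could then reflect who is left in the mean rather than the drug.

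**Working it through.** **1. The visit grid.** From SAP Table 3-1, nominal day = 7 × week + 1 and, from Week 24 on, lower window limit = nominal day − 41. For Week 432: 7 × 432 + 1 = 3025 and 3025 − 41 = 2984, both as printed. There are 38 post-baseline visits: Weeks 2 and 4, plus 36 from Week 12 to Week 432.

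**2. The latest last dose.** PTx is 30 days after the last dose (Protocol 6.5), with a window of ±3 days. The latest last dose is 31 January 2025 − 27 days = 4 January 2025.

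**3. Who can reach the last windows on treatment.** Latest first dose = 4 January 2025 − (lower limit − 1) days.

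| Visit | Lower limit (day) | First dose no later than |
|---|---|---|
| Week 408 | 2816 | 21 April 2017 |
| Week 420 | 2900 | 27 January 2017 |
| Week 432 | 2984 | 4 November 2016 |

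The protocol's approximate maximum gives 7.5 × 365.25 = 2739 days (391 weeks), inside the Week 396 window (2732 to 2815). It corresponds to a first dose of about 6 July 2017. If that maximum holds, Weeks 408, 420 and 432 contain only carried-forward scores.

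**4. One matched pair.** Five years of possible follow-up is Day 1826, inside the Week 264 window (1808 to 1891). Weeks 276 to 432 are 14 further visits. The rule fills a dropout at all 14 and a subject who stays until closure at none.

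**5. Illustration A (assumed inputs).** Let share r of the subgroup be able to reach a visit and let share d have dropped out, with d equal in those who can and cannot reach it.

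- Observed = r(1 − d).
- Carried forward with a cap = rd, so the imputed share is d.
- Carried forward without a cap = d, so the imputed share is d / (d + r(1 − d)).

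| d (share with a cap) | r = 75% | r = 50% | r = 25% |
|---|---|---|---|
| 30% | 36% | 46% | 63% |
| 50% | 57% | 67% | 80% |
| 70% | 76% | 82% | 90% |

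Equal d overstates the excess if subjects with less possible follow-up have had less time to drop out. Illustration B removes that assumption.

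**6. Illustration B (assumed inputs).** Possible follow-up F is uniform from Fmin (2 or 4 years) to 7.5 years, with a constant dropout rate of a per year. At time w in years:

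- Observed = P(F ≥ w) × (1 − a)^w.
- Carried without a cap = the average over F of 1 − (1 − a)^min(w, F).
- Share with a cap = 1 − (1 − a)^w.

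Worked case: a = 10%, Fmin = 2 years, Week 336 (w = 6.44). The share with a cap is 1 − 0.9^6.44 = 49.3%. P(F ≥ w) = (7.5 − 6.44)/5.5 = 0.193, so observed = 0.193 × 0.507 = 9.8%. Carried without a cap = 38.0%. The share without a cap is 38.0/(38.0 + 9.8) = 79.5%.

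| Share from dropouts, no cap vs cap | a = 10% | a = 20% | a = 35% |
|---|---|---|---|
| Week 96, either Fmin | 17.6 vs 17.6% | 33.7 vs 33.7% | 54.7 vs 54.7% |
| Week 240, Fmin 2 y | 51.2 vs 38.4% | 75.5 vs 64.2% | 91.7 vs 86.2% |
| Week 240, Fmin 4 y | 42.7 vs 38.4% | 68.2 vs 64.2% | 88.3 vs 86.2% |
| Week 336, Fmin 2 y | 79.5 vs 49.3% | 93.2 vs 76.2% | 98.6 vs 93.8% |
| Week 336, Fmin 4 y | 74.2 vs 49.3% | 90.8 vs 76.2% | 98.0 vs 93.8% |

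The excess is zero at Week 96, which everyone can reach. It is about 2 to 13 points at Week 240 and 4 to 30 points at Week 336. These are shares of the mean, not bias in the score.

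**The case against.** **The redaction.** The charge rests on the absence of a cap, and the text immediately before the LOCF sentence is blacked out. Redacted text cannot be counted as missing from the plan. This stands: a reader might infer that late means are definitely distorted, but the documents support only that they would be unless the hidden text limits the rule.

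**The outdated duration.** A reader might blame the 432-week sentence. That does not follow, because the sentence drives no calculation and updating it alone would change no number. The cause is uncapped LOCF combined with the closure exception, under a calendar stop or a cutoff.

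**Closure is partly handled.** SAP 6.3 exempts study closure, and Protocol 3.7 ties end of study to country availability or 31 January 2025, so the term can reasonably cover both. This is fair, but the SAP does not define it. If availability exits were coded as premature discontinuation, they would be imputed and the imbalance would shrink. Either way, the exemption does not limit how far other dropouts are carried.

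**Size and consequence.** The illustrative percentages rest on assumed dropout and entry patterns; the documents give no dropout rate, entry dates or subgroup size. The analysis is a descriptive subgroup summary of secondary endpoints with no hypothesis testing. Both points stand, and they limit the weight of the finding.

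**Conclusion.** The concern holds conditionally. On the visible text, the stated rule would over-weight dropouts at visits that some subjects in this subgroup cannot reach, at the final analysis through the calendar stop and at an interim through the data cutoff. The direction follows from the rule for any non-zero dropout, given staggered entry and closure exits left unimputed. The effect on mean CDAI or PRO2 cannot be determined from the documents, and the percentages above are illustrative only.

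It would be too strong to infer that the trial's efficacy or safety results are compromised. Visits every subject can reach are unaffected, the full-population CDAI/PRO2 summary uses observed values, and safety, the primary endpoint, does not use this rule. The change should be made before the final analysis; if the redacted text already holds a suitable cap, confirming that would settle the capping point.

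**What to change.** In SAP 6.3:

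1. State that exits through country availability or the 31 January 2025 end date are study closure and are not imputed.
2. For all other discontinuations, apply LOCF only at analysis visits whose Table 3-1 window opens (first dosing date + lower-limit study day − 1) on or before the earliest of: the country availability date; the last treatment date that allows PTx by 31 January 2025; and, for an interim analysis, the data cutoff date.
3. Show observed and imputed n at each visit.

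Use the window's lower limit rather than the nominal date. In the five-year example, a completer's end-of-treatment scores at about Day 1826 fall in the Week 264 window. A cap on the nominal date (Day 1849) would leave the matched dropout out of that visit and reverse the imbalance.

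In SAP 1.2, bring the 432-week sentence into line with Protocol 3.4 for consistency.

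The cost is SAP text and one derived variable, the latest reachable visit per subject. The downside is fewer subjects in this subgroup's late-visit summaries. The protocol, visits, procedures and sample size do not change.
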